5.2.2 Clinical Studies

Camostat mesilate or Foipan[®], has been approved in Japan since 1985 for the remission of acute symptoms of chronic pancreatitis and postoperative reflux esophagitis. Much of the results and data in this section are from clinical studies presented as part of the Japanese drug approval process.

FOY-251 and GBA were found to be the primary metabolites of camostat mesilate when administered to normal, healthy subjects. FOY-251, the active metabolite, has a half-life in blood of approximately 75 minutes. Plasma kallikrein was suppressed for 2 to 4 hours following administration of camostat mesilate.

Nine studies using camostat mesilate enrolling a total population of 216 subjects with acute, chronic, or postoperative pancreatitis were conducted, with the majority of subjects dosed at 200 mg TID. The duration of dosing ranged from 2 weeks to more than 13 weeks. Few adverse events (AEs) were reported and no serious adverse events (SAEs) were documented from these studies. These studies did not have formal statistical tests, but did show a decrease in serum and urinary amylase levels throughout the treatment period (Kinami et al, 1980; Hirayama et al, 1980a; Abe et al, 1980; Fujiwara et al, 1980; Hayawaka et al, 1980; Hirono, 1980; Horiguchi et al, 1980; Kubota and Meada, 1980; Tanaka and Tsuchiya, 1980).

Two studies by Hirayama et al were conducted on subjects with pancreatitis (Hirayama et al, 1980a, Hirayama et al, 1980b). In both of these studies, camostat mesilate was dosed at 200 mg TID. Both studies showed that camostat mesilate significantly reduced serum and urine amylase levels. Only 1 AE was reported in the camostat mesilate group compared with none in the placebo group.

A PK and safety Phase 1/2 study (NI03-001) is currently being conducted in the United States with 2 phases (Ramsey et al, 2019). In the first phase, a single-dose of camostat mesilate at doses of 100 mg, 200 mg, and 300 mg were administered to 18 subjects with chronic pancreatitis. At all doses, camostat mesilate displayed markedly lower exposure (maximum serum concentration [C_{max}] and area under the curve [AUC]) than the 2 metabolites. 4-GBA exposure appeared to be 2 to 3 times higher than that of FOY-251. Camostat mesilate exposure did not increase as the doses of camostat mesilate increased, which may be explained by the markedly low exposure of camostat mesilate at all doses. FOY-251 exposure increased as the doses of camostat mesilate increased from 100 mg to the 200 mg, but not from the 200 mg to the 300 mg. 4-GBA exposure (both C_{max} and AUC) increased as the doses of camostat mesilate increased from 100 mg to the 200 mg, but only the AUC slightly increased from the 200 mg to the 300 mg. There were no deaths or SAEs, and 3 out of 18 subjects reported 4 treatment-emergent adverse events (TEAEs). Two TEAEs were mild and 2 were moderate in severity, with both of the mild TEAEs considered by the investigator to be possibly related to camostat mesilate. They occurred in the same subject and were an episode of dizziness and one episode of hot flashes after a single dose of 100 mg dose. Three of the TEAEs were reported following a dose of 100 mg camostat mesilate and the fourth TEAE was reported following a dose of 300 mg camostat mesilate. Laboratory hematology and clinical chemistry data showed no trends

following camostat mesilate administration and there were no individual clinically significant abnormalities. Camostat mesilate had no significant effect on heart rate or blood pressure at any dose tested. The data from the first phase of this study suggested that the camostat mesilate is safe to administer to subjects with chronic pancreatitis as a single dose up to and including 300 mg.

The second phase of Study NI03-001 is a randomized, double-blind, placebo-controlled study of 3 doses of camostat mesilate (100 mg, 200 mg, and 300 mg) administered TID for 28 days for the treatment of chronic pancreatitis associated pain. This study is still ongoing and data remain blinded. Six SAEs (nephrolithiasis, diabetic ketoacidosis, abdominal pain [2 events], pancreatitis, pancreatitis acute) have been reported from 3 subjects. All events required hospitalization and each event resolved. All events were considered by the investigator as not related to study drug. All but 1 event occurred in the 28-day follow-up period after the last treatment.

There are no expected concerns of safety for camostat mesilate. The safety profile of this class of drugs is favorable. Two studies done as far back as 1980 in subjects with pancreatitis reported that adverse effects were rare (< 3%), mostly mild, such as pruritus, increased thirst and appetite, and lightheadedness (Abe et al, 1980; Ishii et al, 1980).

5.3 Clinical Risks/Benefits of Camostat Mesilate

Camostat mesilate has been available in Japan for 30 years where it is used for the treatment for relief of the acute symptoms of chronic pancreatitis and postoperative reflux esophagitis. The following is taken directly from the package insert for Foipan[®] (camostat mesilate) and is considered an important precaution:

Foipan Tablet[®] 100 mg should not be administered to patients with severe chronic pancreatitis requiring dietary restrictions such as gastric aspiration, or abstaining from food or drink.

In terms of the AEs seen in humans with chronic pancreatitis, in 3806 subjects subject to reporting of adverse reactions in the clinical trial at the approval stage and in the post-marketing surveillance study, 83 adverse reactions (including abnormal clinical laboratory test values) were observed in 69 of 3806 subjects (1.8%). The main adverse reactions were 15 cases of rash (0.4%), 9 cases of itching (pruritus; 0.2%), 10 cases of nausea (0.3%), 7 cases of abdominal discomfort (0.2%), and 6 cases of abdominal bloating (0.2%).

From a postoperative reflux esophagitis investigation for FOIPAN performed up to the time of approval and in the Drug Use Investigation, 75 AEs were reported in 57 (1.3%) out of 4224 subjects. The major AEs were 12 (0.3%) cases of hepatic function abnormalities such as increased AST and ALT, 8 (0.2%) cases of diarrhea, and 5 (0.1%) cases of nausea.

The Foipan[®] package insert also details the following significant adverse reactions:

Symptoms of Shock and Anaphylaxis

Shock or anaphylactoid symptoms were reported from post-marketing surveillance. No specific antibody production has been reported with the drug in antigenicity studies in animals. However, in view of time course of symptom development (symptoms developed within 30 minutes after dosing in most cases), initial symptoms (dermatitis such as welts, itching sensation, and erythema, vertigo, feeling poorly, dull headache, sweaty, cold sweat, edema/swelling, dyspnea, and decrease in blood pressure), and subjects who had a past history of administration of this drug had experienced symptoms of hypersensitivity (e.g., urticaria, itching sensation and edema), these may have occurred due to anaphylactic reactions.

Thrombocytopenia

Serious decreased platelets have been reported from post-marketing surveillance. Symptoms included subcutaneous hemorrhage, oral hemorrhage, and epistaxis. The number of days until the onset was within 1 month after administration in most cases. Possible idiopathic thrombocytopenic purpura was suspected in some reported cases. In subacute and chronic toxicity studies of the drug, the decrease in platelets was not observed, and the mechanism of pathogenesis remains unknown.

Hepatic Function Disorder, Jaundice

Hepatic function disorder and jaundice (both with unknown frequency), accompanied by extreme elevation of aspartate aminotransferase (AST), alanine aminotransferase (ALT), and gamma-glutamyl transferase (GGT), and alkaline phosphatase (ALP) have been reported from post-marketing surveillance. Initial symptoms included general fatigue, nausea and vomiting, and jaundice. Most of disorders occurred without subjective symptoms and identified by medical examinations. The duration from the beginning of dosage to onset was 12 months in many cases. Some disorders occurred (identified) after the end of administration of the drug. In subacute and chronic toxicity studies of the drug, hepatic function abnormal was not observed, and the mechanism of pathogenesis remains unknown.

Hyperkalemia

Serious hyperkalemia has been reported from post-marketing surveillance, although the frequency is unknown due to spontaneous reporting. Most of the disorders occurred without subjective symptoms and were identified by medical examinations. Abnormal electrocardiograms or electrocardiogram abnormalities with clinical symptoms (general fatigue and sensation of heaviness in chest) were observed in some cases. The duration from the beginning of dosage to the onset was within 2 months in most cases. In subacute and chronic toxicity studies of the drug, abnormal changes in potassium levels were not observed, and the mechanism of pathogenesis remains unknown.

Overall, the evidence of clinical activity and the AE profile observed support a positive benefit-to-risk ratio for subjects with COVID-19 who are treated with camostat mesilate.

Details regarding known or anticipated benefits and risks, as well as reasonably anticipated AEs for camostat mesilate may be found in the IB ([Sagent Pharmaceuticals, 2020](#)).

5.4 Study Rationale

The primary objective is to evaluate the efficacy of camostat mesilate in ambulatory subjects with confirmed COVID-19 infection. Based on the mechanism of action (MOA) of camostat in vitro to inhibit viral entry, subjects with nonsevere disease will be enrolled. Secondary objectives and endpoints include an assessment of efficacy of camostat mesilate evaluating the proportion of subjects requiring COVID-19 related hospitalization or death due to any cause, the overall survival rate, time to hospitalization, resolution of fever, and viral shedding. Safety objectives include assessments of AEs, vital signs, and laboratory parameters.

This study will be executed during a worldwide outbreak of COVID-19, resulting in capacity issues at many medical facilities and concerns about the safety of healthcare providers caring for these sick patients. Consequently, this study is designed to minimize the burden on clinical sites, including minimizing the number of required assessments and interventions, while protecting the safety of participants and retaining scientific rigor.

The investigational product and reference product (placebo) will be identical and indistinguishable to masked study personnel to limit bias in study assessments. Most interventions and assessments may be accomplished in conjunction with the schedule dictated by standard of care (SOC).

6 STUDY OBJECTIVES AND ENDPOINTS

6.1 Study Objectives

6.1.1 Primary Objective

The primary objective of this study is:

- To evaluate the clinical efficacy of camostat mesilate in ambulatory subjects with confirmed COVID-19

6.1.2 Secondary Objectives

The secondary objective of this study is:

- Evaluate the safety profile of camostat mesilate in ambulatory subjects with confirmed COVID-19

6.2 Study Endpoints

6.2.1 Primary Endpoint

- Proportion of subjects requiring COVID-19 related hospitalization (including emergency room visit) or who die due to any cause within 28 days of randomization

6.2.2 Secondary Endpoints

Survival/Mortality

- The overall survival rate (the proportion of randomized subjects who survive up to Day 15 and Day 28)

Clinical Improvement

- Time to resolution of fever from randomization up to Day 28
- Time to hospitalization or death following randomization up to Day 28
- Proportion of subjects with no viral shedding (yes/no) using RT-PCR at Day 7, Day 15, and at Early Termination (for subjects withdrawn prior to completing the 14-day treatment period)

Safety/Tolerability

- Incidence of AEs and SAEs of any grade from randomization up to Day 28
- Cumulative incidence of grade 3 and 4 AEs from randomization up to Day 28
- Incidence of discontinuation from study due to an AE/SAE (discontinued subjects will be followed up until Day 28)
- Change from baseline in clinical laboratory parameters
- Change from baseline in vital signs (heart rate, blood pressure, peripheral capillary oxygen saturation [SpO₂])

7 INVESTIGATIONAL PLAN

[figure not shown]
7.1 Description of Overall Study Design and Plan

This is a randomized, double-blind, placebo-controlled study of camostat mesilate in ambulatory outpatients with confirmed COVID-19 with at least one risk factor for severe illness. Subjects will be randomized in a 2:1 ratio of camostat mesilate:placebo. Approximately 300 subjects are planned to be enrolled (200 subjects to camostat mesilate and 100 subjects to placebo). Subjects will be treated with camostat mesilate 200 mg orally QID for 14 days and receive local SOC in addition to study drug. Subjects in the control arm will receive 2 placebo tablets orally QID for 14 days, as well as local SOC. All subjects will be followed until Day 28. Subjects will complete a symptom eDiary daily from Day 1 (first dose of study drug) through Day 15. Subjects will be coming into the clinic for assessments on Day 1, Day 7 and Day 15. Mid-turbinate nasal samples will be obtained at Screening, Day 7 and Day 15. Instructions for obtaining proper nasal samples will be provided. Subjects who withdraw from the study prior to completion of the 14-day

treatment period will be asked to return for an Early Termination visit for blood draws and a mid-turbinate swab collection. On Day 28 (end of study), a study team member will record subject disposition.

Figure 1 presents the study design.

Figure 1. Study Schematic

Abbreviations: COVID-19 = coronavirus disease 2019; SOC=standard of care.

^a The Screening/Baseline and Day 1 visit assessments can be done on the same day.

7.2 Discussion of Study Design and Dosing

Camostat mesilate will be dosed at 200 mg (two 100 mg tablets) taken orally QID (800 mg/day total) for 14 days. This dosing was selected based on the requirement to have a constant presence of camostat mesilate in the circulation. It is well accepted that after 5 half-lives there is no, or negligible amounts, of drug left in the blood stream. The measurable half-life of camostat is in the region of 75 minutes and therefore 5 half-lives would be 6.25 hours. The approved dose of camostat in Japan is 200 mg TID but taking that dose in the treatment of COVID-19 would only provide coverage for approximately 18 to 19 hours and not the 24 hours coverage that is required. Therefore, a dose of 200 mg QID would theoretically offer 24 hours coverage at some level. In order to have 24 hours coverage of serine protease inhibition, a dose of 200 mg QID is appropriate and would not be expected to cause SAEs, especially if given for a limited period of 14 days. More detailed information can be found in the camostat mesilate IB.

The target population in this study is ambulatory subjects who have confirmed, mild to moderate COVID-19 who have at least 1 risk factor to develop complications. Subjects with mild to moderate disease were chosen because of the known method of action of camostat mesilate to block entry of the SARS-CoV-2 virus into the human cell. Camostat mesilate blocks TMPRSS2, a cellular protein protease that is necessary for SARS-CoV-2 to enter lung cells. It is hypothesized that a drug with this MOA will prevent the worsening and progression of COVID-19 and prevent hospitalization.

7.3 End of Study

A subject will have fulfilled the requirements for study completion if/when the subject has completed all study periods, including the end of study visit on Day 28, which is the last

scheduled visit as indicated in the Schedule of Assessments (Table 1). Subjects who terminate prior to completing the 14-day treatment period are asked to complete the Early Termination visit.

8 SELECTION OF STUDY POPULATION

Section 7.1 provides information regarding number of subjects planned to be enrolled.

8.1 Inclusion Criteria

Individuals must meet all of the following criteria to be included in the study:

1. Adults willing and able to provide informed consent before performing study procedures
2. Adults aged ≥ 18 years at time of informed consent
3. Subjects must have written notification of laboratory confirmed COVID-19 infection performed prior to screening, at a local laboratory by RT-PCR or other commercial or public health assay in any specimen. Subjects should be randomized within 72 hours of receiving this notification.

(NOTE: all subjects will also undergo RT-PCR testing of mid-turbinate samples at a central laboratory on a specimen collected during the Screening/Baseline and Day 1 visit, but entry to the study is based on previously completed local testing for clinical purposes).

4. Have a mild or moderate form of COVID-19 defined as a SpO₂ > 94% at screening
5. Subjects must have at least 1 of the following risk factors for severe illness:
 - a. Aged 65 years or older
 - b. Hypertension
 - c. Diabetes mellitus
 - d. Chronic lung disease including asthma, chronic obstructive pulmonary disease (COPD), and interstitial lung disease (e.g., idiopathic pulmonary fibrosis)
 - e. Chronic cardiac conditions, including coronary artery disease (CAD), heart failure, congenital heart disease, cardiomyopathy
 - f. Severe obesity (body mass index [BMI] ≥ 40 kg/m²)
 - g. Chronic liver disease, including cirrhosis
6. Must agree not to enroll in another study of an investigational agent or take any other drug that has been granted Emergency Use Authorization prior to completion of Day 28
7. If women of childbearing potential (WOCBP) or men whose sexual partners are WOCBP, must be able and willing to use at least 1 highly effective method of contraception during the study and for 90 days after receiving the last dose of study drug. A female subject is considered to be a WOCBP following menarche and until she is in a postmenopausal state for 12 months or otherwise permanently sterile (for which acceptable methods include hysterectomy, bilateral salpingectomy, and bilateral oophorectomy). Contraceptive use by men or women should be consistent with local regulations regarding the methods of

contraception for those participating in clinical studies. Information on contraceptive use during the study is presented in [Appendix 1](#).

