COVID-19 is diagnosed by using reverse transcriptase-polymerase chain reaction (RT-PCR) from a nasopharyngeal swab sample. The sensitivity of this assay is high but not 100%; therefore repeat testing is important if the person continues to exhibit symptoms, has knowingly been exposed, or lives in an area where there are a high number of COVID-19 cases ([Gandhi et al, 2020](#)).

The most common symptoms of a mild to moderate COVID-19 infection are fever, cough, sore throat, malaise, and myalgia. Anorexia, nausea, diarrhea, anosmia, and ageusia are often reported. Dyspnea may occur (usually 5 to 8 days after symptom onset) and is suggestive of more severe disease, often a precursor to hospitalization. Dyspnea can occur in patients with moderate disease but the oxygen saturation is usually at least 94% on room air ([Gandhi et al, 2020](#)). Importantly, clinical deterioration typically does not occur until more than 5 to 7 days following symptom onset, suggesting there is a window of opportunity for antiviral therapy early in the infection prior to the subsequent onset of severe systemic inflammation.

Certain comorbid conditions render a person more susceptible to contracting COVID-19 and contribute to worsening of the disease to a more severe version. These conditions include: age ≥ 65 years, cardiovascular disease, chronic lung disease, hypertension, diabetes, obesity, and diseases that weaken the immune system ([Gandhi et al, 2020](#)).

Patients with mild or moderate COVID-19 are usually instructed to recover at home, where they can be isolated, observed, monitored, and receive supportive care. However, some patient's conditions may deteriorate, especially those with comorbid conditions, which most often happens a week after onset of symptoms. These patients should be monitored closely. Patients with mild to moderate disease are able to monitor their own oxygen saturation levels if they are given a pulse oximeter ([Gandhi et al, 2020](#)).

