8.3 COVID-19 RT-PCR Test at Central Laboratory

Subjects who test positive for COVID-19 at the local laboratory will be enrolled if the subject meets all other entry criteria requirements. Nasal mid-turbinate swab samples are also to be obtained at the Screening/Baseline and Day 1 visit for central laboratory viral testing for COVID-19 as a baseline assessment and to test for viral shedding. If a subjects' test performed at the local laboratory is positive for COVID-19 but the test performed at the central laboratory is negative, the subject will stay in the study and complete all study visits. The reason for this is that RT-PCR testing is not sensitive enough to be accurate 100% of the time. These subjects will provide safety data for camostat mesilate. Statistical analysis for efficacy endpoints may be adjusted for subjects who fall into this category.

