2.5 ANALYSIS SETS

2.5.1 Intent-to-Treat Population (ITT)

The Intent-to-Treat (ITT) population will include all subjects who are randomized. Subjects will be analyzed according to their study treatment assignment, not according to the treatment actually received. The ITT population is the primary population and will be used for evaluating primary and secondary efficacy endpoints and subject baseline characteristics.

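### Inclusion criterion 3 is worded so broadly that a positive antibody test satisfies it, no other criterion enforces current infection, and the SAP omits the protocol's partial safeguard

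*Protocol*

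**What the plan says.** **Entry test.** Protocol 8.1, criterion 3, asks for written notification of laboratory-confirmed infection, established "at a local laboratory by RT-PCR or other commercial or public health assay in any specimen". The synopsis has the same wording. Neither place limits the kind of assay or mentions antibody tests.

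**Timing.** "Subjects should be randomized within 72 hours of receiving this notification". The clock starts when the notification is received, not at sampling or symptom onset.

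**Disease state.** Criterion 4 reads "Have a mild or moderate form of COVID-19 defined as a" SpO2 above 94% at screening. Sections 8.1 and 8.2 require no symptoms, set no limit on time since onset, and do not exclude past infection.

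**Central test.** A baseline swab goes to the central laboratory, but "entry to the study is based on previously completed local testing for clinical purposes". Under 8.3, if the local result is positive and the central one negative, "the subject will stay in the study and complete all study visits". The stated reason is: "The reason for this is that RT-PCR testing is not sensitive enough to be accurate 100% of the time". Section 8.3 adds that the efficacy analysis may be adjusted for such subjects.

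**Analysis.** SAP 2.5.1: "The Intent-to-Treat (ITT) population will include all subjects who are randomized", and this is the primary population. The protocol synopsis, 13.3.1 and 13.3.2 plan a sensitivity analysis in central-laboratory-confirmed subjects. SAP section 1 says that the SAP prevails where the two documents differ.

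**The concern.** The protocol's own background (5.1.1) says: "COVID-19 is diagnosed by using reverse transcriptase-polymerase chain reaction (RT-PCR) from a nasopharyngeal swab sample". The same section describes an early window for antiviral therapy, and 7.2 rests the drug's rationale on blocking viral entry. Criterion 3 is broader than that. A positive serology result on blood is a commercial assay in a specimen, and it may reflect an infection that is over.

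The reason in 8.3 for keeping central-negative subjects is that PCR can miss virus. That presumes the local positive showed current virus, which an antibody result need not do.

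At stake is the share of the ITT set to which the question of treating confirmed COVID-19 does not apply. Such subjects would be expected to contribute little or no treatment effect, so they would reduce the absolute difference and the power.

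**Working it through.** **1. Does another provision close the gap?**

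| Provision | Does it enforce current infection? |
|---|---|
| 72-hour window (8.1) | No. It runs from notification. |
| Criterion 4 (8.1) | Not in operation. It names the disease but tests only SpO2, which a recovered person can meet. |
| Exclusion 1 (8.2) | Only by physician discretion, across up to about 25 sites. |
| Central RT-PCR (8.1, 8.3) | No. It does not gate entry, and central-negative subjects stay. |
| PP2 set (SAP 2.5.3, 4.7) | No. Failing an entry criterion is a major deviation, but a serology entrant meets criterion 3 as written. |
| Central-confirmed sensitivity analysis (Protocol 13.3.1, 13.3.2) | Partial. It leaves randomization and the ITT test unchanged. It is absent from the SAP's analysis sets (2.5), its missing-data and sensitivity section (4.1.7) and shell Table 14.2.1.1. |

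**2. Reproducing the plan's figure.** Inputs from Protocol 13.1: 30% (placebo) and 15% (camostat), two-sided 5% Fisher's exact test, 183 + 92 = 275, 80% power. Enumerating both binomial distributions gives exact power of 0.802, so the stated figure reproduces. At the 200/100 to be randomized, the unadjusted chi-square test of SAP 4.1.1 has exact power 0.853.

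**3. Dilution model.** Let *f* be the share of each arm that entered on serology after clearance, and *b* their event rate, which treatment does not change. Both are assumptions.

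- Arm rate = (1 − *f*) × active-infection rate + *f* × *b*
- Risk difference = (1 − *f*) × 15 points, whatever *b* is

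Example, *f* = 10%, *b* = 0: placebo 0.9 × 30% = 27.0%; camostat 0.9 × 15% = 13.5%; difference 13.5 points.

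Exact power with *b* = 0:

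| *f* | Placebo / camostat | Difference | Chi-square, 200/100 | Fisher, 183/92 |
|---|---|---|---|---|
| 0 | 30.0% / 15.0% | 15.0 points | 0.853 | 0.802 |
| 2% | 29.4% / 14.7% | 14.7 | 0.844 | 0.791 |
| 5% | 28.5% / 14.25% | 14.25 | 0.829 | 0.775 |
| 10% | 27.0% / 13.5% | 13.5 | 0.804 | 0.746 |
| 20% | 24.0% / 12.0% | 12.0 | 0.749 | 0.686 |

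The 183/92 column matters because 13.1 raises 275 to about 300 for drop-out only.

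**4. Sensitivity to *b*.** SAP 3.1 treats any hospitalization or ER visit on the End of Study form as COVID-related, and every subject has a risk factor, so *b* may exceed zero. With *b* = 5%, Fisher power at 183/92 is 0.771, 0.738 and 0.664 for *f* = 5, 10 and 20%. The relative risk is 0.50 when *b* = 0. With *b* = 5% it is 14.0/27.5 = 0.51 at *f* = 10% and 13.0/25.0 = 0.52 at *f* = 20%. The loss is therefore almost wholly in the absolute difference and power.

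**The case against.** The strongest reply is that the text, read as a whole, means active disease. Criterion 3 speaks of laboratory-confirmed infection and not of any positive assay. Criterion 4 says that subjects must have mild or moderate COVID-19, with SpO2 grading a disease they already have. Entry rests on testing done for clinical purposes, the first visit records current symptoms (10.1.1), and a physician may decline a subject under exclusion 1. This stands as evidence of intent. It does not stand as enforcement, because a site following the wording literally could enrol on serology without a deviation.

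Second, the protocol has a safeguard: the central-confirmed sensitivity analysis, and the statement in 8.3 that the efficacy analysis may be adjusted. This stands in part. The analysis addresses subjects without detectable virus at baseline, but it cannot change who is randomized, and the SAP does not carry it forward.

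Third, the size is unknown. No document gives a serology share, and at 2% the loss is about 0.01 in power. At 200/100 by chi-square, power stays at 0.80 even at 10% with *b* = 0. This stands fully.

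A reader might infer that antibody-positive people with past infection are in fact being randomized, or that everyone entered on serology could not benefit. The documents support neither. They show that the wording permits such entry, not that it happens, and a positive antibody result can, but need not, mean that the virus has cleared.

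**Conclusion.** The gap is real but limited. As written, criterion 3 can be met by an antibody result, and nothing else in the entry rules enforces current infection, although the wording suggests that this was intended. For any share above zero whose infection has cleared and whose event rate treatment does not change, the absolute difference shrinks by the factor (1 − *f*) and power falls.

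How far it falls rests entirely on assumed shares. With *b* = 0 and *f* between 2% and 20%, power at 200/100 by chi-square lies between 0.844 and 0.749 (0.853 undiluted), and at 183/92 by Fisher between 0.791 and 0.686 (0.802 undiluted). The true share may be at or below the low end, where the effect is negligible. The point does not show that the trial is underpowered. It merits a change because the repair is nearly free and because the one analysis that would reveal the problem is missing from the SAP.

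**What to change.** 1. Reword criterion 3 in Protocol 8.1 and the synopsis to: RT-PCR or other assay that detects SARS-CoV-2 nucleic acid or antigen; antibody (serology) results do not qualify. The specimen wording can stay, since limiting the specimen type would narrow entry more than the problem requires.
2. Record the assay type of the qualifying test on the eCRF, so that the share in question can be reported.
3. Restore the central-laboratory-confirmed sensitivity analysis in the SAP for the primary and secondary efficacy endpoints, with a row in shell Table 14.2.1.1.

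Cost: one sentence in two places, one eCRF field and one SAP analysis on data already planned; no new test. Candidates with only a serology result are not enrolled. The rewording does not address a late RT-PCR positive, because the 72-hour clock would still run from notification; the restored analysis would not identify these subjects if their central test is also positive.
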